### **3.1 STUDY OUTCOME MEASURES**

The primary outcome measure will be the reported NRS (numeric rating score) score which is validated score to assess pain and anxiety levels with values from 0-11. The patient will be asked to fill out the NRS score prior to the hysteroscopy and following the hysteroscopy prior to leaving the clinic.

Secondary outcome measures will be length of procedure, complication rate, reported side effects, procedure completion, hysteroscopy findings and type of procedure performed (for example if purely diagnostic or if any operative procedures are performed).

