## **1.2 RATIONALE FOR CURRENT STUDY**

The purpose of this study would be to determine if the use of VR technology can reduce pain and anxiety experienced by patients during outpatient hysteroscopy procedures when compared to standard pain management.

The optimal method of controlling pain and anxiety during outpatient hysteroscopy is poorly understood and there is a wide variation in clinical practice. This study aims to test whether VR technology could reduce pain and anxiety as a relatively simple and safe adjunct to conventional pain management. Although VR has been used in a variety of clinical settings to date, there is only one previous study investigating the use of VR in an outpatient hysteroscopy setting (Deo et al 2020). This existing trial established that the use of VR is feasible in the OPH setting and that it was effective with significant improvements in patient reported anxiety and pain scores compared to conventional pain management. However, as the authors themselves acknowledge, it involved relatively small numbers (20 patients in control and intervention group respectively). The rationale of this study would be to build upon this evidence by performing the first large scale adequately powered randomised control trial of the use of VR technology in this setting.

We hypothesise that the use of VR technology will significantly improve pain and anxiety when compared to conventional pain management. Finding additional low risk ways of improving pain and anxiety during OPH is of critical importance in order to improve patient experience and the success rate of the procedure as pain is a major reason for unsuccessful OPH procedures.

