## **2. STUDY OBJECTIVES**

The primary objectives of this study are to determine if:

- 1) VR technology can reduce pain during outpatient hysteroscopy?
- 2) VR technology can reduce anxiety during outpatient hysteroscopy?

The secondary objectives of this study are to determine if:

- 1) The use of VR technology feasible during outpatient hysteroscopy?
- 2) The use of VR during outpatient hysteroscopy reduces the procedure failure rate?
- 3) The use of VR increases the outpatient hysteroscopy appointment time?

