### 3. STUDY DESIGN

The study design is an unblinded randomised controlled trial. This study design was chosen as it will provide the best quality of evidence with reduced bias compared to other study designs. A randomised controlled trial is also very feasible in this scenario. Neither the researchers nor the participants will be blinded as to which study arm they are in, as it would be impractical to do so with a VR headset used in the intervention group. The study will be adequately powered with a power calculation based upon findings from previous studies, meaning at least 40 patients will be included in each arm (at least 80 patients in total).

Patients will be randomly allocated by computer allocation to either the intervention or the control group. The intervention group will undergo OPH with standard care plus the use of VR technology administered through a headset with the option of wearing headphones (at the patient's discretion) or having the accompanying sound played aloud. The control group will undergo outpatient hysteroscopy with standard care. Standard care in this unit is in line with the RCGOG guidelines and involves advising patients to take ibuprofen and/or paracetamol one hour prior to their procedure unless there are contraindications. Local anaesthetic intracervical block is used at the discretion of the operator and is usually used if dilatation of the cervix is required.

The primary outcome measure will be the reported NRS (numeric rating score) score which is validated score to assess pain and anxiety levels with values from 0-11. The patient will be asked to fill out the NRS score prior to the hysteroscopy and following the hysteroscopy prior to leaving the clinic.

Secondary outcome measures will be length of procedure, complication rate, reported side effects, procedure completion, hysteroscopy findings and type of procedure performed (for example if purely diagnostic or if any operative procedures are performed).

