At the time of their hysteroscopy. The patient will fill out the pre-procedure NRS score prior to entering the hysteroscopy room. The patient will then enter the outpatient hysteroscopy room where there will be the hysteroscopy team consisting of the lead hysteroscopist and the assistant, and also a single member of the research team who will have taken the study consent from the patient prior to their procedure. Following discussion with the hysteroscopist as usual, the patient will prepare for the procedure and position themselves on the procedure couch. Once comfortable, the member of the research team will help the patient to put on the VR headset (See appendix 1), and if the patient wishes, headphones. The virtual reality software will then start running and is controlled by the research team member, the software will run for the length of the procedure. The hysteroscopy team will be preparing the equipment as the virtual reality software is running. The member of the research team will remain in the room throughout the procedure to troubleshoot any issues with the headset or software and if necessary to stop the VR program. Following completion of the procedure the patient will fill out a NRS score prior to going home.

The VR software involves breathing exercises, relaxing music and a distracting immersive walk through a virtual environment. The scenario will be started and subsequently controlled by a member of the research team operating a tablet device. The hysteroscopy team will perform the procedure in exactly the same way as they would normally and any clinical decisions regarding potential procedures such as polypectomy, discontinuing or proceeding with the hysteroscopy will be made by the hysteroscopy team along with the patient in the usual way without any input from the research team member.

Maintaining appropriate clinical hygiene is of critical importance as the same headset will be used for different patients. The headset can be easily and effectively cleaned between use and the manufacturer (VR medical) provides a recommended cleaning regimen which we will use for the trial. After use, the VR device and controller should be cleaned with a damp microfibre cloth and disinfectant wipe, both the parts that have been in contact with the skin and the headbands.

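### Does the post-procedure NRS need a written reference period and a fixed completion time before it can measure pain and anxiety during hysteroscopy?

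*Combined protocol and SAP*

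**What the plan says.** Section 1.2 gives the purpose as finding out whether VR can "reduce pain and anxiety experienced by patients during outpatient hysteroscopy procedures", and supports it by noting that "pain is a major reason for unsuccessful OPH procedures". Section 2 sets two primary objectives: whether "VR technology can reduce pain during outpatient hysteroscopy" and whether "VR technology can reduce anxiety during outpatient hysteroscopy".

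Section 3.1 names the NRS as the primary outcome and asks the patient to "fill out the NRS score prior to the hysteroscopy and following the hysteroscopy prior to leaving the clinic". Section 3 repeats that rule ("following the hysteroscopy prior to leaving the clinic"), and its account of the procedure day says: "Following completion of the procedure the patient will fill out a NRS score prior to going home". For the headset, Section 3 states that "the software will run for the length of the procedure".

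The list of recorded data in Section 3 has one pain NRS item and one anxiety NRS item, with no label for worst, average or current level. Section 4.2 requires patients to be able to complete an NRS questionnaire, and Section 6 ends the study once the last post-procedure questionnaire is filled in. Section 7 compares mean NRS scores between groups with an unpaired t test.

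**The concern.** The objectives are about the procedure, while the outcome is defined only by when the form is filled in. VR stops when the procedure ends. A patient who rates how she feels on leaving is therefore describing a time when the intervention is no longer running and the painful stimulus has passed. Such a rating would satisfy the wording of Section 3.1 without answering either objective. If some patients rated the procedure and others rated the present moment, the t test in Section 7 would average two different quantities.

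The pre-procedure rating makes this reading plausible. It is taken before the patient enters the room, so it can only describe her current or anticipatory state, and the later rating uses the same score with no changed instruction in the text.

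The loss could not be repaired afterwards. A rating of the procedure that is not collected on the day is gone, and without a recorded completion time the spread of recall intervals could not be described.

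**Working it through.** The question is mainly one of reading, so the relevant places are set side by side.

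**1. Is a reference period stated anywhere?** The NRS appears in eight places: the Study Summary, Section 3 (the design paragraph, the account of the procedure day and the data list), Section 3.1, Section 4.2, Section 6 and Section 7. That is 1 + 3 + 1 + 1 + 1 + 1 = 8. The number that state the period rated is 0. This overstates the gap a little. The design paragraph of Section 3 and Section 3.1 carry the same sentence, and an eligibility criterion (4.2) or a test specification (7) is not where a recall period would be expected.

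**2. Is an interval set?** Three places time the later rating: two in Section 3 and one in Section 3.1. None gives a number of minutes. All three do bound it to the same visit, after the procedure and before departure.

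**3. Is the completion time collected?** The data list in Section 3 has 9 bulleted and 6 unbulleted items, 15 in all. Two are procedure times (length of procedure, time in the procedure room) and none is the NRS completion time. The list also omits reported side effects, which Section 3.1 names as a secondary outcome, so it may be incomplete. The text supports *not listed*, not *not recorded*.

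**4. What does the rest of the protocol say about the period?** The title, the aim in the Study Summary, the purpose in Section 1.2 and both objectives in Section 2 all refer to pain and anxiety during the procedure. A form completed straight after a procedure, in a trial with those aims, is most naturally read as asking about that procedure.

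**5. Can a size be attached?** No. The protocol gives at least 40 patients per arm but no effect size, standard deviation or power. For scale only, assume a two-sided 0.05 level and 80% power. The detectable standardised difference is then

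(1.960 + 0.842) × √(2/40) = 2.802 × 0.2236 = 0.626.

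Now assume that a rating of current state on leaving keeps a share *f* of that difference. Power is approximately Φ(*f* × 0.626 / 0.2236 − 1.960):

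| Assumed share *f* | Power at 40 per arm |
|---|---|
| 1 | 80% |
| 0.75 | 56% |
| 0.50 | 29% |
| 0.25 | 10% |

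The starting power and *f* are both assumptions, and the table applies only if every patient rates her current state. It shows what that reading would cost, not that the reading will occur, and it carries no weight in the conclusion.

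**The case for a change.** The strongest case for acting is that intent is not an instruction. The word *during* in the objectives tells the reader what the investigators want to know. It does not tell a patient what to rate or a staff member when to hand out the form. This is the only measure serving both primary objectives, the trial is unblinded and the outcome is self-reported. One sentence in Section 3.1 and one recorded time would need no extra patients or visits.

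Part of this stands. The protocol would be clearer with the rated period and the summary (worst or average level) written down, and the single appendix, which shows the headset and controller, does not supply them.

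The rest does not carry. The wording put to patients belongs on the questionnaire, which is not available here, so the documents show that the protocol text omits the period, not that the trial has left it undefined. If the form asks about the procedure, a same-visit window is a defensible choice. The timing rule is the same in both arms, and nothing suggests long or uneven delays. Asking for a set interval without being able to say which one, or what bias it removes, is asking for more detail rather than offering a better method. Section 8.1 reports ethics approval as already obtained, so even a small textual change would mean an amendment.

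Whether Section 7 compares post-procedure scores or changes from the pre-procedure score is also unstated. That is a separate question, and treating the post-procedure score as the primary outcome is the natural reading rather than an explicit statement.

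**Conclusion.** The omission is real, but no change to the plan follows. It is a definition left unwritten, which the investigators and analysts can fill from the stated objectives and the questionnaire: the post-procedure scores are ratings of pain and anxiety experienced during the hysteroscopy just completed. Checking that the form says so, and reporting its wording with the results, is ordinary housekeeping. A fixed interval and a logged completion time would be refinements.

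The consequence ranges from none, if the form asks about the procedure, to a different question being answered, if every patient rates her state on leaving. The documents do not place the trial within that range. The conclusion rests on two assumptions: that the questionnaire follows the objectives, and that the time between the end of the procedure and completion does not differ materially between arms. Nothing in the protocol contradicts either. A form that asked only about the present moment would reopen the point.

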**STUDY SUMMARY**

**TITLE** Does Virtual Reality Technology Reduce Pain and Anxiety During Outpatient Hysteroscopy? A Randomised Controlled Trial

**DESIGN** Randomised controlled trial

**AIMS** To evaluate whether the use of virtual reality technology can reduce pain and anxiety during outpatient hysteroscopy procedures.

**OUTCOME MEASURES** Primary outcome measures are patient reported NRS (numeric rating score) for pain and anxiety.  
Secondary outcome measures will be length of procedure, complication rate, reported side effects, procedure completion or if stopped, hysteroscopy findings and type of procedure performed.

**POPULATION** Women aged referred from general gynaecology clinics for outpatient hysteroscopy procedures.

**ELIGIBILITY** Inclusion criteria are age 18-70, capacity to give informed consent and cognitive and linguistic ability sufficient to understand and fill out the NRS questionnaire. Exclusion criteria are epilepsy or severe vertigo, blindness or significant hearing impairment and recent facial injury/burn

**DURATION** 1 year

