The timetable for the project is expected to run as follows. Three months for preparation and obtaining ethical approval. Recruitment is expected to start following this and we would expect to obtain the required number of participants by 3 months based on the average referral rate for outpatient hysteroscopy in the unit being 150 patients per month and a 20% study participation rate. Data analysis and preparing the final report would take a further 3 months.

Results will be recorded onto a pseudoanonymised database. Information will be collected from patients notes and imaging reports. Each patient will be allocated a study number and for each the following will be recorded:

- Age
- Parity
- Symptoms and duration
- Past medical history and co-morbidities
- BMI
- Previous surgery
- Current medication and medication used within the last 6 months
- Pain NRS (numeric rating score)
- Anxiety NRS

Length of hysteroscopy procedure  
Time in Outpatient Procedure room  
Procedure successfully completed (or not) and reason for failure if appropriate  
Complications  
Hysteroscopy findings  
Type of hysteroscopic procedure performed

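### Side effects are a named secondary outcome with no item in the per-patient data list and no defined way of asking, so capture may be incomplete or unequal between arms

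*Combined protocol and SAP*

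**What the plan says.** **Outcome.** Section 3.1 reads "Secondary outcome measures will be length of procedure, complication rate, reported side effects, procedure completion", then adds hysteroscopy findings and type of procedure. Section 3 and the Study Summary carry the same outcome. None of the three defines a side effect or says how or when it is ascertained.

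**Data list.** Section 3 says "Each patient will be allocated a study number and for each the following will be recorded" and gives 15 items. Complications are among them; side effects are not. On sources it says "Information will be collected from patients notes and imaging reports".

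**Patient-completed form.** The only one described is the NRS: "Following completion of the procedure the patient will fill out a NRS score prior to going home".

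**Observation.** Section 3 says "Neither the researchers nor the participants will be blinded as to which study arm they are in", and, in describing the VR session, "The member of the research team will remain in the room throughout the procedure to troubleshoot any issues with the headset or software".

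**Adverse events.** Section 5.1 defines an adverse event broadly enough to cover minor symptoms. Sections 5.3 and 5.3.1 require all of them to be reported, and the non-serious ones recorded whether or not they were expected. No arm is exempt.

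**Claim in the rationale.** Section 1.2 presents the study as a test of whether "VR technology could reduce pain and anxiety as a relatively simple and safe adjunct to conventional pain management".

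**The concern.** An outcome that is announced but has no field in the database and no form behind it is either not collected or collected ad hoc. For mild, short-lived symptoms, what gets recorded depends heavily on whether someone asks, and this plan does not say that anyone asks, or that both arms are asked alike.

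The stake is how the result would be read. The rationale describes VR as relatively safe and low risk, and Section 4.3 excludes epilepsy and severe vertigo, which suggests that headset-related symptoms were foreseen. Without a defined method, a low count could mean good tolerability or little questioning, and an excess under VR could mean harm or closer observation. Such symptoms may not be recoverable afterwards.

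**Working it through.** **Step 1. Match each secondary outcome in Section 3.1 to the data list in Section 3.**

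| Secondary outcome | Item in the data list |
|---|---|
| Length of procedure | Yes |
| Complication rate | Yes |
| Side effects | None |
| Procedure completion | Yes, with reason for failure |
| Hysteroscopy findings | Yes |
| Type of procedure | Yes |

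Five of six have an entry.

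**Step 2. Could another item stand in?** Complications cannot, because the protocol lists the two as separate outcomes. The symptoms-and-duration item sits between parity and past medical history, so it most naturally means presenting symptoms. The reason for failure would catch only a symptom that ended the procedure.

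**Step 3. Does Section 5 close the gap?** In part. It gives a duty to record that applies to both arms. It names no question, time point or person who asks, and does not say that these records supply the secondary outcome.

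**Step 4. Is capture equal by arm?** Not assured. Section 3 has a research team member in the procedure room without limiting this to one arm, but the sentence on remaining throughout is tied to the headset and software. Presence throughout for controls is not stated, and nothing requires the same questions in both arms.

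**Step 5. Size, by illustration.** The plan gives no figure for side effects, so there is none to reproduce. The one input from the documents is at least 40 patients per arm (Section 3). The true rate *p* and the share captured *c* are assumptions, shown over a range.

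Expected recorded cases in one arm = 40 × p × c. Probability that none is recorded = (1 − p × c)^40.

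| True rate p | c = 100% | c = 50% | c = 25% |
|---|---|---|---|
| 5% | 2 expected; 12.9% | 1; 36.3% | 0.5; 60.5% |
| 10% | 4; 1.5% | 2; 12.9% | 1; 36.3% |
| 20% | 8; below 0.1% | 4; 1.5% | 2; 12.9% |

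With full capture, at least one case would be seen with probability 1 − 0.95^40 = 0.871 at a 5% rate and 1 − 0.90^40 = 0.985 at 10%. So 40 patients are enough to see a common symptom if it is asked about.

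For unequal capture, suppose the true rate is 20% in both arms, with 80% captured in one and 40% in the other. Recorded rates are 0.20 × 0.80 = 16% and 0.20 × 0.40 = 8%, a false difference of 8 points. At a true rate of 10% it is 4 points, and at 30% it is 12 points. The sign depends on which arm is observed more closely.

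**The case against.** The strongest reply is that a recording route exists. Section 5 covers any untoward occurrence in either arm, so a symptom that comes to light should be written down. That stands, and it narrows the point to two gaps: no method of asking, and no link from Section 5 to this outcome.

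A reader might infer more than this, and the documents do not support it:

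- *That collection is by spontaneous report and nobody asks.* The plan is silent. The same adjective is applied to the NRS, which is actively requested.
- *That side effects must come from hospital notes.* Notes and imaging reports cannot be the only source, because the same list contains the patient-completed NRS.
- *That controls are unobserved.* Section 3 leaves the researcher's presence throughout for controls unclear rather than absent, and an assistant is part of the hysteroscopy team.

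It is also fair that the capture shares above are invented for illustration, that no direction of bias is established, and that a modest distortion would not pass for a finding. Four of 40 against two of 40 gives a two-sided Fisher p of about 0.68: with six events in total, only the 3–3 split is more probable than the observed split, so p = 1 − C(40,3)²/C(80,6) = 1 − 0.325. That limits the risk of a false significance claim. It does not make the recorded rates interpretable.

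Finally, Section 2 has no safety or tolerability objective. That holds down the priority, but side effects remain a declared outcome.

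**Conclusion.** The point holds in limited form. Side effects are a declared secondary outcome without a data item or a defined method of collection, and the general adverse event rule does not supply either. In an unblinded trial they *may* be under-recorded or recorded unequally; it does not follow that they *will* be. The comparison, as planned, could not support a tolerability statement in either direction.

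The missing item and method can be seen from the text and rest on no assumption. The numerical size does: over assumed true rates of 5% to 20%, halving capture from complete moves the chance of recording no case among 40 VR patients from 12.9% to 36.3% at the low end, and from below 0.1% to 1.5% at the high end. The pain and anxiety outcomes are not affected. This is a cheap improvement, not a threat to the trial's main result.

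**What to change.** 1. Add a side-effects item to the per-patient data list in Section 3.
2. Give both arms the same short yes/no symptom checklist before they leave the clinic. The investigators should settle the items; nausea, dizziness, headache, visual discomfort, faintness and other would be a starting list.
3. Put it on a separate sheet or section, completed only *after* the post-procedure pain and anxiety NRS. Asked beforehand, prompts about symptoms could influence the primary ratings.
4. Define the outcome as the proportion with each symptom, reported by arm.
5. Leave adverse event reporting under Section 5 as it is.

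The cost is about one extra minute per patient, one more data item and a minor amendment. More mild symptoms will be reported, so the tolerability figures may look slightly less favourable.
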